# 11.7.1 Assessing Relationship to Study Treatment

The following should be considered when assessing the relationship of an AE to study treatment:

- Temporal relationship of the onset of the event to the first dose of tazemetostat
- The course of the event, considering especially the effect of discontinuation of study treatment or the reintroduction of study treatment, as applicable
- Whether the event is known to be associated with the study treatment or with other similar treatments
- The presence of risk factors in the study subject known to increase the occurrence of the event
- The presence of non-study treatment-related factors that are known to be associated with the occurrence of the event.

The relationship of an AE to study treatment is to be classified as follows:

- **Not Related:** A causal relationship between tazemetostat and the AE is not a reasonable possibility.
- **Related:** A causal relationship between tazemetostat and the AE is a reasonable possibility (includes probably, possibly and definitely related).

If the causal relationship between an AE/SAE and tazemetostat is related, that determination will be used for purposes of expedited regulatory reporting.

# 11.8. Outcome Categorization

Outcome of an AE/SAE may be classified as resolved, resolved with sequelae, unresolved or death.

All treatment-related AEs/SAEs will be followed to resolution (the subject's health has returned to his/her baseline status or all variables have returned to normal), or until an outcome is reached, stabilization occurs (the investigator does not expect any further improvement or worsening of the event), or the event is otherwise explained, regardless of whether the subject is still participating in the study. Where appropriate, medical tests and examinations will be performed to document resolution of the event(s).

# 11.9. Timeframe for Reporting AEs and SAEs

**AEs:** AEs will be collected from the time the first dose of study treatment is administered until the earlier of either 30 days after the discontinuation of study treatment or until the initiation of subsequent anti-cancer therapy.

**SAEs:** SAEs will be collected over the same time period as stated above for AEs. In addition, any SAE assessed **as related** to study participation (e.g., protocol-mandated procedures, invasive

tests, or change in existing therapy), study treatment must be recorded from the time a subject provides consent to participate in the study up to and including any follow-up contact. All SAEs will be reported to the sponsor within 24 hours.

After discontinuation of study treatment: The investigator will monitor all ongoing AEs/SAEs until resolution or stabilization of the event or until the subject is lost to follow-up or has withdrawn consent. Up until 30 days after the last dose of study treatment or until the initiation of subsequent anti-cancer therapy, whichever is earlier, the Investigator will report any AE that they consider to be possibly related to study treatment.

Note that any incidence of secondary lymphoma, even if occurring more than 30 days after the last dose of study drug, will be reported to the Sponsor as an SAE.

### 11.10. Reporting of SAEs

All SAEs will be reported within 24 hours of the investigator becoming aware of the event. The investigator must promptly notify the sponsor or its designee of all SAEs in order that the legal obligations and ethical responsibilities of the sponsor or its designee are met.

The sponsor has a legal responsibility to notify both the local regulatory authority and other regulatory agencies about the safety of the IP under clinical investigation. The sponsor and its designee will comply with country specific regulatory requirements relating to safety reporting to the regulatory authority, IRB/EC/CEC and investigators.

Any AE that is both unexpected (not consistent with the applicable product information) and also meets the definition of a serious adverse event/reaction would be considered a suspected unexpected serious adverse reaction ("SUSAR"). All SUSARs will be reported within 24 hours of the Investigator becoming aware of the event. SUSARs are prepared for expedited reporting according to local regulatory requirements and are forwarded to Investigators as necessary. The Sponsor is legally obligated to report the event to the regulatory authorities within 7 days for fatal or life-threatening SUSARs or 15 days for all others.

An investigator who receives an investigator safety report describing a SAE(s) or other specific safety information (e.g., summary or listing of SAEs) from the sponsor will file it with the IB and will notify the IRB/EC/CEC, if appropriate according to local requirements.

#### 11.10.1 Regulatory Authorities, IRB/EC, and CECs

The sponsor or its designee is responsible for notifying the investigational sites of all expedited SAEs. The sponsor or designee shall also notify Central Ethics Committees (CEC) of new serious, related, and unexpected AE(s) or significant risks to subjects, per country requirements.

The investigator will notify the IRB/EC/CEC of serious, related, and unexpected AE(s) or significant risks to subjects, per local country requirements. The investigator must keep copies of all AE information, including correspondence with the sponsor or local IRB/EC/CECs on file.

It is the responsibility of the Principal investigator to notify the IRB/EC of all SAEs that occur at his/her site. Investigators will be notified of all suspected, unexpected SAEs (7/15-Day Safety Reports) that occur during any clinical studies that are using the investigative compound. Each site is responsible for notifying their IRB/EC/CEC of these additional SAEs.

All studies that are conducted within any European country will comply with the European CTD 2005/28/EC and CTD 2001/20/EC. All SUSARs will be reported as required to the Competent Authorities of all involved European member states.

#### 12. DATA MANAGEMENT

Data from eCRFs and other external data will be entered into an Electronic Data Capture clinical database. These data will be electronically verified through the use of real-time checks processed during data entry, and through programmed edit checks as specified in the data management plan. Discrepancies in the data will be brought to the attention of the clinical team and investigational site personnel, if necessary, in the form of an electronic data query. Resolutions to these issues will be reflected in the database and an audit trial within the system will track all queries and changes made to the data. Quality control audit(s) will be performed.

#### **12.1. Coding**

Concomitant medications will be assigned a code using the version of the World Health Organization (WHO) dictionary (version June 2015 or higher) drug codes specified in the data management plan (version June 2015 or higher). Concomitant medications will be further coded to the appropriate Anatomical-Therapeutic-Chemical (ATC) code indicating therapeutic classification. A listing of concomitant medications by drug and drug class will be included in the CSR for this protocol.

AEs will be classified into standardized terminology from the verbatim description (investigator term) according to the version of the Medical Dictionary for Regulatory Activities (MedDRA) coding dictionary (version 18.0, or higher) specified in the data management plan. AEs will be presented by Preferred Term (PT) nested within System Organ Class (SOC). Verbatim description and PT and SOC MedDRA-level terms for all AEs will be contained in the data listings of the CSR for this study.

# 13. STATISTICAL METHODS

#### 13.1. Hypotheses

For Part 2 of the study, the null hypothesis is that DCR rate after 12 weeks of treatment (percentage of subjects with a CR, PR or SD at the Week 12 tumor assessment), as assessed at the Stage 2 analysis, is not clinically meaningful (≤20%). The alternative hypothesis is that the DCR rate at 12 weeks is clinically meaningful (≥35%) and, therefore, the study treatment warrants further development. At the Stage 1 analysis, 30 subjects will be enrolled and treated, and the analysis and decision rules specified here are based on 30 subjects. For the Stage 1 analysis with 30 treated subjects, at least five CR+PR+SDs are needed for the part to declare a success i.e., to have demonstrated sufficient clinical activity. At the end of the study, if there are 17 or more CR + PR +SDs out of 55 treated subjects, then the new treatment is accepted.

### 13.2. Study Design Considerations

### **13.2.1** Determination of Sample Size

The sample size of 12 subjects for Part 1 is sufficient for an initial assessment of the PK and safety profiles of the 400 mg tablet.

For Part 2 of the study, evaluation will be done using a Green-Dahlberg two-stage design, to allow early termination of the study due to the lack of efficacy. The sample size is calculated on the primary endpoint. The hypothesis will be tested using a one-sided test with  $\alpha$ =0.05 and the type II error rate will be controlled at 0.2. The numbers of subjects to be enrolled using a Green-Dahlberg two-stage design is listed in the table below.

Green-Dahlberg	CR + PR + SD at 12 Weeks
Stage 1 Sample Size (n1)	30
Stage 1 Rejection of Drug (r1)	4
Maximum Sample Size (n) a	55
Stage 2 Rejection of Drug (r)	16

CR = complete response; PR = partial response; SD = stable disease a. The interim analysis planned at the end of Stage 1 may occur sooner if the Stage 1 rejection criterion is surpassed before all 30 subjects are treated and followed for 12 weeks. In this scenario, the total sample size (Stage 1 + Stage 2) would still remain unchanged at 55 subjects.

Approximately 30 subjects will be enrolled and treated in Stage 1 (see Section 13.3.2, Interim Analyses, for further details). While evaluating the response for the first 30 treated subjects, the enrollment and treatment of subsequent subjects will be continued. If the study continues on to Stage 2, a total of 55 subjects will be enrolled in the entire study.

- The probability of early stopping under the null hypotheses is 0.255.
- The probability of early stopping under the alternative hypotheses is 0.008.

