### Statistical methods

**Sample size rationale:** The sample size of 12 subjects for Part 1 is sufficient for an initial assessment of the PK and safety profiles of the 400-mg tablet. The sample size in Part 2 is calculated on the primary endpoint using a two-stage Green-Dahlberg design. The hypothesis will be tested using a one-sided test with  $\alpha$ =0.05 and the type II error rate will be controlled at 0.2.

Null Hypothesis: CR + PR + SD at 12 weeks  $\leq 20\%$ Alternative Hypothesis: CR + PR + SD at 12 weeks  $\geq 35\%$ 

Green-Dahlberg	CR + PR + SD at 12 weeks
Stage 1 Sample Size (n1) a	30
Stage 1 Rejection of Drug (r1) a	4
Maximum Sample Size (n)	55
Stage 2 Rejection of Drug (r)	16

a. The interim analysis planned at the end of Stage 1 may occur sooner if the Stage 1 rejection criterion is surpassed before all 30 subjects are treated and followed for 12 weeks. In this scenario, the total sample size (Stage 1 + Stage 2) would still remain unchanged at 55 subjects.

- At the End of Stage 1, if there are ≤4 CR + PR + SD out of 30 subjects, then reject the new treatment and terminate the study for futility. If there are ≥5 CR + PR + SD out of 30 subjects, the study continues to Stage 2.
- At the end of the study, if there are ≤16 CR + PR +SD out of 55 subjects, then reject the new treatment. When there are ≥17 CR + PR + SD out of 55 subjects, then the new treatment is accepted.
- The probability of early stopping under the null hypotheses is 0.255.
- The probability of early stopping under the alternative hypotheses is 0.008.

**Table 1:** Study Assessments

	Screening a	Cycle 1	Cycle 1	Cycles 2 – 8	Cycles 9 +	Post- Treatment/ Early Termination q	Follow-up r
Study Days	Days -21 to -1	Day 1	Days 8 & 15 (±1 day)	Day 1 & every 21 days (±3 days)	Day 1 & every 42 days (±3 days)	(±3 days)	
Procedures/Assessments b							
Informed consent	X						
Inclusion/exclusion criteria c	X	X					
Demographics	X						
Medical History	X						
Prior and concomitant medications				Throughout the	study		
Physical examination - Complete	X	X		X	X	X	
Physical examination - Symptom directed			X				
Weight	X	X		X	X	X	
Height	X						
Vital signs d	X	X	X	X	X	X	
ECOG performance status	X	X	X	X	X	X	
12-lead ECGs e	X	X	X	X	X	X	
Pregnancy test f	X	X		X	X	X	
Hematology g	X	X	X	X	X	X	
Blood chemistry g	X	X	X	X	X	X	

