### 13.3.2 Interim Analyses

If, in consultation with the investigators, the PK and safety profiles of tazemetostat in Part 1 are acceptable, then the 400 mg tablets will be used in Part 2.

For Part 2, the decision rules at the end of Stage 1 are listed in the table below.

	Part 2 (Relapsed/Refractory Synovial Sarcoma)
Null Hypothesis	CR+PR+SD at Week 12 ≤20%
Alternative Hypothesis	CR+PR+SD at Week 12 ≥35%
Stage 1 Sample Size (n1)	30
Stage 1 Rejection of Study Treatment (r1)	4

The end of Stage 1 occurs when the first 30 treated subjects have completed at least the Week 12 assessment, completed the final study visit or terminated early from the study, whichever is sooner.

- At the end of Stage 1, if there are ≤ 4 CR + PR + SD out of 30 subjects, then reject the new treatment and terminate the study for futility. When there are ≥5 CR + PR + SD out of 30 subjects, the study continues to Stage 2.
- At the end of the study, if there are ≤16 CR + PR +SD out of 55 treated subjects, then reject the new treatment. When there are ≥17 or more CR + PR +SD out of 55 subjects, then the new treatment is accepted.

The interim analysis planned at the end of Stage 1 may occur sooner if the Stage 1 rejection criterion is surpassed before all 30 subjects are treated and followed 12 weeks. In this scenario, the total sample size (Stage 1 + Stage 2) would still remain unchanged at 55 subjects.

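### Minor: the stated decision rule has a type II error of 0.221 (power 77.9%) at a DCR of 35%, not the 0.2 at which the plan says it is controlled

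*Combined protocol and SAP*

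**What the plan says.** Section 13.2.1 sets a one-sided test at α = 0.05 and states that "the type II error rate will be controlled at 0.2". The Synopsis, under Statistical methods, repeats this ("type II error rate will be controlled at 0.2"). The hypotheses are a Week 12 DCR of at most 20% against at least 35%.

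The rule is the same wherever it appears (Synopsis, 13.1, 13.2.1 and 13.3.2):

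- Stage 1: 30 subjects; stop for futility at 4 or fewer with disease control, continue at 5 or more.
- End of study: "if there are 17 or more CR + PR +SDs out of 55 treated subjects, then the new treatment is accepted"; with 16 or fewer the treatment is rejected.

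Two operating characteristics are printed to three decimals. Early stopping has probability 0.255 under the null, and "The probability of early stopping under the alternative hypotheses is 0.008". The attained type I error and power of the rule are not given.

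**The concern.** A two-stage rule with whole-number cut-offs has one exact type II error at a given true rate, and it can be checked directly. Saying that the error is controlled at 0.2 tells the reader that the chance of wrongly rejecting the drug at a DCR of 35% is no more than 20%. That figure is also the stated basis for the sample size of 55. If the rule does not deliver it, the sample size justification describes a property the design does not have, and the sponsor or the monitoring committee would take the false-rejection risk to be lower than it is.

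Nothing elsewhere supplies a margin. Missing and non-evaluable responses count as not controlled (13.4.1), and Part 2 subjects are not replaced (10.6).

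**Working it through.** **Inputs, all from the protocol**

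- Null rate p₀ = 0.20 and alternative p₁ = 0.35, the least favourable point of the range at or above 35% (13.1)
- Stage 1: n₁ = 30, r₁ = 4; total n = 55, r = 16 (13.2.1)
- One-sided α = 0.05, type II error 0.2 (13.2.1)
- No early acceptance. Passing Stage 1 leads to Stage 2, and the total stays at 55 even if the interim look is brought forward (13.3.2).

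**Step 1: reproduce the plan's own figures.** With X₁ ~ Bin(30, p), the probability of stopping early is P(X₁ ≤ 4).

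| True DCR | Exact | Printed in 13.2.1 |
|---|---|---|
| 20% | 0.2552 | 0.255 |
| 35% | 0.0075 | 0.008 |

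Both agree, so the exact binomial model with these boundaries is the one behind the plan.

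**Step 2: probability of accepting the treatment.** With X₂ ~ Bin(25, p),

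P(accept | p) = Σ over x₁ = 5,…,30 of P(X₁ = x₁) × P(X₂ ≥ 17 − x₁).

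| True DCR | P(accept) | Meaning |
|---|---|---|
| 20% | 0.0367 | type I error, within 0.05 |
| 35% | 0.7793 | power |
| 35.5% | 0.8015 | |
| 36% | 0.8222 | |

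The type II error at 35% is 1 − 0.7793 = 0.2207. It splits into 0.0075 from stopping at Stage 1 and 0.2131 from ending with 16 or fewer of 55 after continuing (the parts sum to 0.2207 before rounding). Power equals 0.80 at a true DCR of 35.47%.

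**Step 3: where the shortfall arises.** With no interim look, P(X ≥ 17 of 55) at 35% is 0.7797. The futility look therefore costs 0.7797 − 0.7793 = 0.0004. The final cut-off accounts for the rest.

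**Step 4: can 55 subjects meet both limits?**

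- Keeping Stage 1 and accepting at 16 or more of 55 gives power 0.855 but type I error 0.069, which breaks the 0.05 limit.
- At a final cut-off of 17, no futility look can raise power above the single-stage 0.7797.
- A search over all two-stage futility rules with a total of 55 and α ≤ 0.05 finds a maximum power of 0.7820. That case (stop at 15 or fewer of 52, accept at 16 or more of 55) is degenerate: any trial that continues has already met the final criterion, so it is really a 52-subject single-stage test.

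No 55-subject rule of this type reaches 0.80.

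**Step 5: size.** 0.2207 − 0.2 = 0.0207, or 2.1 percentage points. Since 1/0.0207 ≈ 48, this is about one extra false rejection per 48 trials at a true DCR of exactly 35%.

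**The case against.** The case for leaving the text alone has three parts.

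*Rounding.* The type II error is printed as 0.2, to one decimal, and 0.221 rounds to 0.2. The three-decimal figures nearby are attained probabilities, whereas 0.2 is a design target. This is the best defence, but it does not carry. Saying that an error rate is controlled at a value sets a ceiling, the attained rate is above it, and a reader will translate 0.2 into 80% power.

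*Approximate planning.* Two common approximations do reach 80% at n = 55: 0.830 with null and alternative variances, and 0.807 with the arcsine transformation. They may explain how 55 was chosen. Neither describes a cut-off of 17 out of 55. At that cut-off the continuity-corrected normal approximation gives 0.782, and the printed early-stopping figures match the exact binomial.

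*Materiality.* The excess is about two points, the type I error has room to spare, and half a percentage point on the true DCR restores 80% power. This stands in full and is why the point is minor. It does not make the sentence correct.

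It is also fair to say that rewording is not the only remedy. Keeping 30 and 4 at Stage 1 and accepting at 17 or more of 56 gives type I error 0.0431 and power 0.8059.

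**Conclusion.** The statement is wrong as written, by a small amount. The rule has an exact type II error of 0.2207 (power 77.9%) at a DCR of 35%, against a stated limit of 0.2. Its type I error of 0.0367 is within 0.05, and both printed early-stopping probabilities are right.

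The result assumes independent subjects with a common DCR, exactly 30 and 55 subjects in the denominators, and the boundaries as stated. It is evaluated at a true DCR of exactly 35%; for rates of about 35.5% and above, power is at least 80%. The decision rule, the planned analyses and any conclusion from the trial are unaffected.

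**What to change.** In the Synopsis (Statistical methods) and in 13.2.1, replace the statement about the type II error with the attained values, for example: the decision rule has an exact one-sided type I error of 0.037 and exact power of 77.9% (type II error 0.221) at a Week 12 DCR of 35%. Boundaries and enrolment stay as they are. The cost is one sentence in two places and a slightly less favourable stated power.

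If the sponsor prefers to keep the 0.2 limit, a total of 56 with the same Stage 1 rule and the same cut-off of 17 would meet it (Stage 2 of 26 instead of 25). That means one more subject and a change to the sample size wherever it is stated. For a shortfall of this size, rewording is the more proportionate choice.

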### 13.2.2 Sample Size Re-Estimation

The sample size will not be re-estimated during this study.

### 13.3. Data Analysis Considerations

### 13.3.1 Analysis Populations

The Intent-to-Treat (ITT) population will consist of all subjects who receive at least one dose of tazemetostat. The ITT population will be used for summaries and analysis of the efficacy endpoints.

The **Safety Population** will consist of all subjects in the ITT population who have at least one post-dose safety observation recorded. The Safety Population will be used for summaries and analysis of the safety and tolerability.

The **Pharmacokinetic** (**PK**) **population** set will include all subjects in the ITT population who have sufficient post-dose samples collected to allow estimation of the PK parameters. The PK population will be used for PK analysis.

The **Pharmacodynamic (PD) population** will include all subjects in the ITT population who have sufficient samples collected to allow estimation of the PD parameters. The PD population will be used for summaries and graphs of PD data.

### 13.3.2 Interim Analyses

If, in consultation with the investigators, the PK and safety profiles of tazemetostat in Part 1 are acceptable, then the 400 mg tablets will be used in Part 2.

For Part 2, the decision rules at the end of Stage 1 are listed in the table below.

	Part 2 (Relapsed/Refractory Synovial Sarcoma)
Null Hypothesis	CR+PR+SD at Week 12 ≤20%
Alternative Hypothesis	CR+PR+SD at Week 12 ≥35%
Stage 1 Sample Size (n1)	30
Stage 1 Rejection of Study Treatment (r1)	4

The end of Stage 1 occurs when the first 30 treated subjects have completed at least the Week 12 assessment, completed the final study visit or terminated early from the study, whichever is sooner.

- At the end of Stage 1, if there are ≤ 4 CR + PR + SD out of 30 subjects, then reject the new treatment and terminate the study for futility. When there are ≥5 CR + PR + SD out of 30 subjects, the study continues to Stage 2.
- At the end of the study, if there are ≤16 CR + PR +SD out of 55 treated subjects, then reject the new treatment. When there are ≥17 or more CR + PR +SD out of 55 subjects, then the new treatment is accepted.

The interim analysis planned at the end of Stage 1 may occur sooner if the Stage 1 rejection criterion is surpassed before all 30 subjects are treated and followed 12 weeks. In this scenario, the total sample size (Stage 1 + Stage 2) would still remain unchanged at 55 subjects.

# 13.3.3 Key Elements of the Analysis Plan

Complete details of the analysis plan will be provided in the Statistical Analysis Plan (SAP). Any deviations from, or additions to, the original analysis plan in this protocol will be documented in the SAP and the CSR.

All data up to the time of study completion/withdrawal from the study will be included in the analysis, regardless of treatment duration.

Since the duration of study treatment for a given subject will depend on efficacy and tolerability, the duration of follow-up will vary among subjects. All available time-to-event data will be analyzed using appropriate statistical methods. Subjects with shorter treatment and follow-up will not be considered to have missing data. Consequently, there will be no imputation for missing time-to-event data.

Demographics and baseline characteristics will be summarized by study part and overall.

